4.1 Study Arms

4.1.1 Treatment Arm

Bridge auricular therapy will be given in addition to standard of care. Research coordinators that have been trained in placing the Bridge device will apply the device in the immediate post-operative setting (post-anesthesia care unit, PACU). The device will be attached according to the instructions for use provided. Pain scores using a numerical scale will be collected at rest and movement, as well as total opioid consumption and the device tolerability.

4.1.2 Control Arm

Same treatment as in the active arm with the only exception being the use of a sham Bridge device. The sham Bridge device will be identical in appearance to the active device but will have no electrical current and no electrode needles.

4.2 Study Endpoints

The study endpoints are designed to evaluate the impact of Bridge on pain scores and amount of opioids consumed.

[figure not shown]
4.2.1 Primary Endpoints

The primary study endpoints are the change in pain scores and opioid consumption from the day of surgery through post-operative day 5 between sham and active groups.

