3 STUDY OBJECTIVES

The aim of this research is to gather data regarding the feasibility of the Bridge system for the management of pain following total hip arthroplasty (THA; a.k.a. total hip replacement).

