8 STATISTICAL PLAN

8.1 Sample Size

This study may enroll up to 60 subjects. Descriptive statistics will be presented as mean \pm SD. Continuous variable will be reported as median (95 % confident interval). Using SPSS, a one tailed unpaired t-test will be performed to assess the difference in pain between groups. Overall difference between groups over the 5 days will be assessed using an analysis of variance as follows: by Performance test. [REDACTED]

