8.2 Acceptance criteria

The primary outcome measured will be the total opioid consumption for the 5 day period following surgery. Secondary outcome will include pain, PONV, and functional recovery at 24, 48, 72, 96 and 120 hrs post operatively. The subject will be asked to rate the tolerance of the device using a 1-5 scale (1 being extremely poorly tolerated and 5 being extremely well tolerated) every postoperative day until day 5. Safety and Adverse Events not related to the surgery or the hip implant will be collected postoperatively every day for the first 5 days, and at 1 week and 1 month.

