12.4 Protocol Amendments

Any changes made to the clinical investigational plan/study protocol will be documented by way of an amendment. Before submitting protocol amendment to the IRB for approval, the protocol amendment must be agreed upon and signed by both the Investigator and the Sponsor. The Investigator shall not make any changes to the protocol without Sponsor approval and documented approval from the IRB. Both PI and Sponsor will retain the IRB approval letter and approved protocol as confirmation that the protocol amendment was approved.

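### Sections 4.2.1 and 8.2 disagree on the primary endpoint: pain over the first 5 days is primary in one and secondary in the other

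*Combined protocol and SAP*

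**What the plan says.** Section 4.2.1 (Primary Endpoints) has two primaries: "The primary study endpoints are the change in pain scores and opioid consumption from the day of surgery through post-operative day 5", compared between the sham and active groups.

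Section 8.2 (Acceptance criteria, within the Statistical Plan) has one: "The primary outcome measured will be the total opioid consumption for the 5 day period following surgery". Its next sentence places pain elsewhere: "Secondary outcome will include pain, PONV, and functional recovery at 24, 48, 72, 96 and 120 hrs post operatively".

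Three other places bear on the question, and none settles it:

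- Section 4.2 introduces all the endpoints with "The study endpoints are designed to evaluate the impact of Bridge on pain scores and amount of opioids consumed". It names both outcomes without ranking them.
- Section 4.2.2 lists daily changes in NRS pain from the day of surgery to day 30 as secondary. That span includes the 5-day window that 4.2.1 treats as primary.
- Section 8.1 says "a one tailed unpaired t-test will be performed to assess the difference in pain between groups" and "Overall difference between groups over the 5 days will be assessed using an analysis of variance". The first sentence concerns pain only. The second does not name its outcome in the visible text. The end of 8.1 is redacted.

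**The concern.** The primary endpoint fixes which comparison carries the trial's main conclusion. Here a reader of 4.2.1 and a reader of 8.2 would report different primary results from the same data. If pain favours the device and opioid consumption does not, 4.2.1 supports calling the pain result primary. If pain does not favour the device and opioid consumption does, 8.2 supports calling pain secondary. Pain can thus move in or out of the primary set after the data are seen.

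Section 8.1 adds to the difficulty. The only test it visibly ties to an outcome is for pain, the outcome that 8.2 makes secondary.

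**Working it through.** **The sections side by side**

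| | Section 4.2.1 | Section 8.2 |
|---|---|---|
| Opioid consumption, first 5 days | primary | primary |
| Pain, first 5 days | primary (change in scores) | secondary (at 24, 48, 72, 96, 120 h) |
| Window | day of surgery through day 5 | 5 days after surgery |

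The opioid row agrees and the pain row does not. The windows match in substance but not exactly. Counted in calendar days, day 0 through day 5 is 6 days, whereas 24 to 120 hours is 5 periods of 24 hours.

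**What the choice changes (illustration only)**

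The documents give no figure to reproduce: no alpha, power or effect size is visible. The inputs below are assumptions.

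- One-sided 0.05 per test, so the critical value is z = 1.645. The plan states one-tailed testing for pain only.
- Two test statistics, Z1 for opioid consumption and Z2 for pain, bivariate normal with correlation ρ = 0, 0.3, 0.5 or 0.8.
- No true effect on either outcome.

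Formulas:

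- Both positive: B = P(Z1 > 1.645 and Z2 > 1.645). At ρ = 0, B = 0.05 × 0.05 = 0.0025.
- Either positive: 0.05 + 0.05 − B. At ρ = 0 this is 0.10 − 0.0025 = 0.0975.
- Pain positive, opioid not: 0.05 − B. At ρ = 0 this is 0.0475.
- Holm, at least one false positive: the smaller p-value must fall below 0.025, so the rate is 0.025 + 0.025 − P(Z1 > 1.960 and Z2 > 1.960). At ρ = 0 this is 0.05 − 0.025² = 0.0494.

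| ρ | Opioid alone primary | Either suffices | Pain positive, opioid not | Both must succeed | Holm |
|---|---|---|---|---|---|
| 0 | 5% | 9.75% | 4.75% | 0.25% | 4.9% |
| 0.3 | 5% | 9.3% | 4.3% | 0.7% | 4.8% |
| 0.5 | 5% | 8.8% | 3.8% | 1.2% | 4.5% |
| 0.8 | 5% | 7.5% | 2.5% | 2.5% | 3.9% |

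The fourth column is the excess over 5%: the chance that pain alone is positive and can be called primary under 4.2.1.

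At one-sided 0.025 per test, the either-suffices rate is 4.9% to 3.9% against 2.5%. These equal the Holm column, because both use z = 1.960.

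**Power cost of keeping both primary**

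Assume each endpoint has 80% power alone at one-sided 0.05, so its mean z is 1.645 + 0.842 = 2.487.

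- Holm, per endpoint: P(Z1 > 1.960) + P(1.645 < Z1 < 1.960 and Z2 > 1.960).
- Both must succeed: P(Z1 > 1.645 and Z2 > 1.645). At ρ = 0 this is 0.80 × 0.80 = 0.64.

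| ρ | Holm, per endpoint | Holm, at least one | Both must succeed |
|---|---|---|---|
| 0 | 77% | 91% | 64% |
| 0.3 | 76% | 87% | 67% |
| 0.5 | 76% | 84% | 69% |
| 0.8 | 75% | 79% | 73% |

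If the other endpoint has no effect, an endpoint under Holm has about 70% power at every correlation in the table.

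**The case against.** - **Feasibility.** Section 3 says "The aim of this research is to gather data regarding the feasibility of the Bridge system", and enrolment is up to 60. This lowers the stakes. But section 1.1 states an aim of investigating effectiveness, section 4 describes a randomized, blinded, sham-controlled design, and section 8.1 plans a between-group test. Such a plan still needs one answer to which result is primary.
- **Redaction.** The end of 8.1 is blacked out and could hold an alpha level, a sample-size basis, a hierarchy or a multiplicity rule. This stands as a limit: I do not say that such a rule is missing, and the either-suffices figures apply only if none is hidden there. A multiplicity rule would still leave 4.2.1 and 8.2 assigning pain different status.
- **Different purpose.** Section 8.2 is headed as acceptance criteria and speaks of pain at time points, where 4.2.1 speaks of change in scores. One could read it as naming only the acceptance measure. That reading is strained, because 8.2 makes its own primary and secondary split and sets no acceptance threshold.
- **Inflation is not certain.** Section 4.2.1 does not say that either endpoint suffices. If both must succeed, the false-positive rate with no effect on either is below 5%. This is correct, and it shows that the plan needs to state the rule.

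**Conclusion.** The concern holds. Two current, complete statements give 5-day pain different status, and no visible text ranks them. The conflict is confined to pain, since 5-day opioid consumption is primary in both sections.

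This conclusion rests on the text alone. The size of the consequence rests on assumed alpha, sidedness and correlations: up to 4.75 percentage points of extra false-positive risk if either endpoint suffices at one-sided 0.05, and a conservative test if both must succeed. It should be fixed before unblinding, because a choice made afterwards would not be credible.

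**What to change.** Amend the protocol before unblinding so that 4.2.1 and 8.2 name the same primary endpoint or endpoints. There are two options.

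1. **Single primary.** Total 5-day opioid consumption is primary, as 8.2 already says, and pain is secondary in both sections. The cost is that pain loses primary status.
2. **Two primaries with a stated rule.** Either both must succeed, or Holm is applied. The cost is the power loss tabulated above: joint power of 64% to 73% if both must succeed, or about 70% to 77% per endpoint under Holm, for endpoints with 80% power alone.

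Under either option:

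- Give one definition of the opioid measure, with its start and end.
- Align the pain entry in 4.2.2 with the choice, since its window overlaps.
- Confirm which test applies to opioid consumption and which outcome the analysis of variance covers. This is a query only, because the end of 8.1 is redacted.

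Section 12.4 sets the procedure: "Any changes made to the clinical investigational plan/study protocol will be documented by way of an amendment", signed by the investigator and the sponsor and approved by the IRB.

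A separate minor point can go in the same amendment. Tolerability is on a 1-10 scale from one phone call at day 5 in 4.2.2, but on a 1-5 scale every postoperative day to day 5 in 8.2. These should be reconciled.

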4.2.2 Secondary Endpoints

Secondary end points will include opioid consumption from the day of surgery to 30 days post-op, daily changes in pain using the Numeric Rating Scale (NRS) on a scale 0-10 from the day of surgery through post-operative day 30, incidence of post-operative nausea and vomiting (PONV), time to oral intake, time to ambulation, time to discharge from the recovery room, time to discharge from the hospital, and the tolerability of the device using a numeric scale from 1-10 obtained via a follow up phone call 5 days after the surgery.

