7.3.2 Intraoperative

The surgery will be performed under spinal plus sedation. Intraoperative patient management will be according to standard of care protocol.

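### The pain endpoint is worded as a change from the day of surgery with no reference score defined; a reference taken after device placement would subtract early device effect

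*Combined protocol and SAP*

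**What the plan says.** Section 4.2.1 gives the primary endpoints as "the change in pain scores and opioid consumption from the day of surgery through post-operative day 5", contrasted between the sham and active arms. Section 4.2.2 adds, as a secondary endpoint, "daily changes in pain using the Numeric Rating Scale (NRS) on a scale 0-10 from the day of surgery through post-operative day 30". Neither says which score the change is measured from.

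Two events fall on the day of surgery. Section 7.3.2 states: "The surgery will be performed under spinal plus sedation". Section 4.1.1 says that trained coordinators "will apply the device in the immediate post-operative setting (post-anesthesia care unit, PACU"). The same section says: "Pain scores using a numerical scale will be collected at rest and movement". The endpoint sections do not say which of the two is tested.

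The statistical sections describe something else. Section 8.1 plans a one-tailed unpaired t-test of the difference in pain between groups and an analysis of variance over the five days. It mentions neither a change score nor a baseline covariate in its visible part. Section 8.2 makes the five-day opioid total the primary outcome and lists pain as secondary, at 24, 48, 72, 96 and 120 hours.

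**The concern.** Read literally, 4.2.1 and 4.2.2 subtract a day-of-surgery pain score from later scores. A post-operative score on that day is taken while the spinal is wearing off, so it is likely to be low and only weakly related to later pain. Unless it is read before placement, the device is already in use. If the device works early, part of its effect then sits in the reference and is subtracted from the result. A device acting within hours would show a smaller change than one acting late.

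The word change also does not suit opioid use, which is a quantity accumulated over a period and has no starting value.

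With the reference undefined, an analyst could choose a level, a change from day 0 or a change from a pre-operative score after seeing the data.

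**Working it through.** **No plan figure to reproduce.** Section 8.1 gives a maximum of 60 subjects. No significance level, effect size, SD or correlation is visible, and part of the section is redacted. What follows is an illustration.

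**Inputs**
- 30 per arm: 60 subjects, 1:1 allocation assumed.
- One-sided test: section 8.1. The 5% level is assumed.
- True difference d = 0.65 SD of a single score: assumed, chosen because it gives 80% power for the unadjusted level.
- Correlation ρ between reference and later score: assumed, 0 to 0.7.
- Fraction f of the effect already in the reference: assumed, 0 (clean) or 0.25.

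**Formulas** (variance of a single score set to 1)
- Level: expected difference d, variance 1.
- Change score: expected difference (1 − f)d, variance 2(1 − ρ).
- Level adjusted for a clean reference: expected difference d, variance 1 − ρ².
- Variance ratio, change to adjusted: 2(1 − ρ)/(1 − ρ²) = 2/(1 + ρ).
- Power: noncentral t, 58 degrees of freedom, noncentrality (expected difference/SD) × √(30/2). The one degree of freedom spent on the covariate is ignored.

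**Example at ρ = 0.2.** The change variance is 2 × 0.8 = 1.60 and the adjusted variance is 1 − 0.04 = 0.96, a ratio of 1.67. Noncentrality for the clean change is 0.65/√1.60 × √15 = 1.99, giving power 0.63. With f = 0.25 the expected difference is 0.75 × 0.65 = 0.4875, the noncentrality 1.49 and the power 0.43. For the adjusted level the noncentrality is 0.65/√0.96 × √15 = 2.57, giving 0.81.

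| ρ | Change, f = 0 | Change, f = 0.25 | Level, unadjusted | Level, adjusted (clean) | Variance ratio |
|---|---|---|---|---|---|
| 0.2 | 0.63 | 0.43 | 0.80 | 0.81 | 1.67 |
| 0.5 | 0.80 | 0.59 | 0.80 | 0.89 | 1.33 |
| 0.7 | 0.94 | 0.78 | 0.80 | 0.97 | 1.18 |

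At ρ = 0 the variance ratio is 2.0.

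**What follows**
- A clean change score has the larger variance than adjustment at every correlation below 1, because 2/(1 + ρ) exceeds 1.
- Against the unadjusted level, a clean change score loses only when 2(1 − ρ) > 1, that is, ρ < 0.5. At 0.5 they tie; above it the change score is better.
- An early effect in the reference shrinks the expected difference to (1 − f)d at any correlation.

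**The case against.** The strongest reply is that no baseline is subtracted at all. The from-through phrase in 4.2.1 can mark an observation window. It also governs opioid consumption, which has no baseline, and 4.2.2 uses near-identical words as a plain window: "opioid consumption from the day of surgery to 30 days post-op". The closing reference to sham and active groups suggests that change may loosely mean a difference between arms. Sections 8.1 and 8.2 fit that reading and already treat opioid use as a total.

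This stands as a fair alternative, but it does not rescue the wording. As a window, 4.2.1 leaves change without a meaning. In 4.2.2, "daily changes in pain using the Numeric Rating Scale (NRS) on a scale 0-10 from the day of surgery" reads more naturally as change from day 0.

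A reader might infer more than the documents support, in three ways.
- **That the baseline is contaminated.** The day of surgery includes time before the operation and before placement. Parts of 7.3.1, 7.3.3 and 7.3.5 are redacted or unreadable and Table 1 is not shown, so a pre-device score may be specified there.
- **That the spinal biases the comparison.** It acts in both arms. It can lower the day-0 score and weaken its correlation with later pain, but does not itself bias a randomized contrast.
- **That a change score loses power even with a clean baseline.** Against an unadjusted level this is true only for correlations below 0.5.

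Testing pain on movement rather than at rest is a preference that the documents do not settle. The need is only to name one, and the redacted text may already do so.

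**Conclusion.** The concern holds in conditional form. The visible text defines no reference score for the change in pain, and 4.2.1 does not match 8.1 and 8.2 on how pain is analysed or on whether it is primary. If the literal wording is followed with a post-device reference, the estimate is attenuated in proportion to the early effect it contains.

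Under the assumed inputs, a quarter of the effect in the reference lowers change-score power from 0.63 to 0.43 at correlation 0.2 and from 0.94 to 0.78 at 0.7. Adjusting a level for a clean pre-device score gives 0.81 to 0.97 over the same range, never below the unadjusted t-test's 0.80. These sizes rest on assumed allocation, significance level, effect, correlation and early-effect fraction. The table also uses the same correlation for the reference and the adjusting score, and a pre-operative score may correlate differently. The direction of the attenuation and the efficiency ordering at a given correlation do not depend on the particular values chosen.

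The sponsor should make this change: it is inexpensive and removes the ambiguity on either reading.

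**What to change.** - In 4.2.1 and 4.2.2, define pain as a post-operative NRS level, for example the mean over the 24 to 120 hour time points in 8.2, and name rest or movement in advance. In 4.2.2, likewise report the later days to day 30 as levels.
- In 8.1, replace the unadjusted t-test with a between-arm comparison adjusted for an NRS score taken before device placement, and state when that score is taken relative to surgery, spinal and placement.
- Define opioid use as the five-day total, as 8.2 does, and drop the word change for it.
- Reconcile 4.2.1 and 8.2 on whether pain is primary or secondary.

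The cost is wording, plus one pre-device NRS reading if the schedule does not already have it. Results would be reported as adjusted levels rather than changes. A 24 to 120 hour mean leaves day-0 pain out of the endpoint; if early relief is of interest, day-0 scores can be reported separately as levels.

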4.2.2 Secondary Endpoints

Secondary end points will include opioid consumption from the day of surgery to 30 days post-op, daily changes in pain using the Numeric Rating Scale (NRS) on a scale 0-10 from the day of surgery through post-operative day 30, incidence of post-operative nausea and vomiting (PONV), time to oral intake, time to ambulation, time to discharge from the recovery room, time to discharge from the hospital, and the tolerability of the device using a numeric scale from 1-10 obtained via a follow up phone call 5 days after the surgery.

6 SUBJECT SELECTION AND WITHDRAWAL

6.1 Number of Subjects

Up to 60 subjects will be enrolled in this study with a potential interim review of the data after 30 patients.

6.2 Inclusion Criteria

- Subject is 18 years of age or older
- Subject scheduled for elective primary unilateral total hip arthroplasty (THA)
- Subject opioid use is less than 60 milligram morphine equivalent for the last 30 days
- Subject has given written informed consent to participate in the study

6.3 Exclusion Criteria

- Subjects with a PROMIS Anxiety raw score of >19
- Subjects who are pregnant or breastfeeding
- Subjects with cardiac pacemakers or other implanted devices (e.g. vagal nerve simulators)
- Subjects with hemophilia
- Subjects with Psoriasis vulgaris
- Subjects with a history of active depression, anxiety or catastrophizing
- Subjects with active alcoholism or drug abuse
- Subjects with severe chronic pain condition that requires daily preoperative opioid dependence
- Subjects deemed not suitable for the study at the discretion of the principal investigator
- Subjects who are concurrently participating in any other research study

6.4 Study Timelines

Each individual subject will actively participate for the duration of approximately 5 days. There will be a follow-up phone interview at POD 7 and POD 30. This study is anticipated to require up to 6 months for completion of patient enrollment.

6.5 Subject Status

Subjects will be classified according to the following statuses:

- Screened – all subjects who met inclusion criteria per chart review and approached for consent.
- Enrolled – all subjects who went through the informed consent process and signed the informed consent form.

- Screen Failure – subjects who do not meet all eligibility criteria after giving informed consent. Upon determination that the subject does not meet all eligibility criteria, the reason for the subject's ineligibility will be documented on the Screening and Enrollment Log.
- Completed – subjects who wear the Bridge device for 120 hours, and complete all assessments through post-operative day 5.
- Withdrawn – subjects who do not complete study either because they voluntarily choose not to participate further in the study and withdraw their consent, or they are discontinued from the study per PI discretion.
- Lost to Follow-up – subjects who are unreachable for assessments during the 1 week and/or 1 month post-operative follow-up. This includes subjects who completed study or were withdrawn from the study but did not withdraw their consent. Subjects will be classified as lost to follow-up if study staff is not able to reach them after three attempts.

6.6 Subject Withdrawal

All enrolled subjects have the right to withdraw their consent at any time during this study. All data collected until the time of subject withdrawal will remain in the study database and will be used for analysis. If a subject is withdrawn from the study, the reason for withdrawal will be recorded on the CRF.

6.7 Subject Discontinuation by Investigator

An Investigator may discontinue a subject from the study, with or without the subject's consent for any reason that may, in the Investigator's opinion, negatively affect the well-being of the subject, subject non-compliance, or if the IRB stops the study for any reason. If a subject is discontinued from the study, the Investigator will promptly inform the subject. The reason for discontinuation will be recorded on the CRF.

